6.5. Post-treatment Assessments

6.5.1. End of Study Visit (all Cohorts)

30 days after the last administration of study drug, subjects will return to the study center to complete an end of study visit. For the purpose of scheduling the end of study visit, a \pm 3 days window may be used. The following evaluations and/or procedures will be performed at the end of study visit for all cohorts, unless otherwise specified:

- 6.5.1.1. Review of AEs and changes in concomitant medication
- 6.5.1.2. Symptom-directed physical examination as needed
- 6.5.1.3. Weight
- 6.5.1.4. Urine collection for the following laboratory procedures:
 - 6.5.1.4.1. Urinalysis
 - 6.5.1.4.2. Urine pregnancy test (females of childbearing potential only, if not done within the previous 30 days).
- 6.5.1.5. Stool sample collection for microbiome analysis (if subject is able to provide) **(Cohorts 5 to 9 only)**. CCI [REDACTED]
- 6.5.1.6. Blood sample collection for the following laboratory analyses:
 - 6.5.1.6.1. Chemistry profile: alkaline phosphatase, AST, ALT, total bilirubin, direct and indirect bilirubin, total protein, albumin, CPK, bicarbonate, BUN, calcium, chloride, creatinine, glucose, phosphorus, magnesium, potassium, sodium, uric acid
 - 6.5.1.6.2. Estimated glomerular filtration rate according to the Cockcroft-Gault formula for creatinine clearance
 - 6.5.1.6.3. Hematology profile: complete blood count (CBC) with differential and platelet count
 - 6.5.1.6.4. Plasma HIV-1 RNA (TaqMan[®] v2.0)
 - 6.5.1.6.5. CD4+ cell count
 - 6.5.1.6.5.1. CD8+ cell count, CD4/CD8 ratio and CD4 % **(Cohorts 5 to 9 only)**
 - 6.5.1.6.6. Cell-associated HIV-1 RNA/DNA (CAVR/CAVD) with stored PBMC

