Cohorts 5 to 9

Day -13 (**Pre-Baseline**)
Day 1 (**Baseline/Dose 1**), Day 2, Day 3, Day 8
Day 15 (**Dose 2**), Day 22
Day 29 (**Dose 3**), Day 31, Day 36
Day 43 (**Dose 4**), Day 45, Day 50
Day 57 (**Dose 5**), Day 58, Day 59, Day 64
Day 71 (**Dose 6**), Day 73, Day 78
Day 85 (**Dose 7**), Day 87, Day 92
Day 99 (**Dose 8**), Day 101, Day 106
Day 113 (**Dose 9**), Day 115, Day 120
Day 127 (**Dose 10**), Day 128, Day 129, Day 134
Day 157 (**End of Study**)

Subjects who prematurely discontinue study drug will be required to complete an Early Study Drug Discontinuation Visit within 30 days after their last dose of study treatment.

The Pre-Baseline/Day -13 visit has an allowable window of ± 3 days.

- Visits scheduled for 2, 4, 7, or 10 days after a Dosing visit, **except for Day 2, 3, 58, 59, 128 and 129** have an allowable window of ± 1 day.

The Day 101 and 157 visits have an allowable window of ± 3 days.

Non-dosing visits may occur at the investigator site or at other location agreed by the subject and mobile nurse vendor.

Screening Procedures:

Screening procedures include: complete physical examination, vital signs, height, weight, medical history (including route and estimated duration of HIV infection, pre-ART viral set point, and complete ARV history), HIV-1 RNA, ARV trough PK, hematology, serum chemistry, serum pregnancy test, urinalysis, HBV and HCV serologies, eGFR, and electrocardiogram (ECG). Pre-ART CD4 nadir and historical genotype will be collected if available.

In order to establish eligibility, Investigators may repeat screening procedures or laboratory assessments for subjects who have an acute illness or abnormal laboratory value that is expected to resolve without sequelae within the screening window.

On-Study Procedures:

Dosing:

For **Cohorts 1 to 3**, dosing visits will occur at Day 1, Day 15, Day 29, Day 43, Day 57, and Day 71. For **Cohorts 4 to 9**, dosing visits will occur at Day 1, Day 15, Day 29, Day 43, Day 57, Day 71, Day 85, Day 99, Day 113 and Day 127. CCI

For **Cohorts 1 to 4**, subjects will fast for at least 2 hours before dosing. For **Cohorts 5 to 8**, subjects will fast overnight (at least 8 hours) before dosing. CCI

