The Investigator will verify the subject's continued eligibility for dosing at post-Baseline dosing visits, including the absence of dose-limiting toxicities (DLTs) and (for females of childbearing potential) a negative urine pregnancy test, prior to dosing. All doses will be directly administered by blinded site staff. Subjects will fast for 2 hours after dosing for all cohorts. After Dose 1, subjects will remain on site for 12 hours after dosing for safety assessment and phlebotomy.

Safety:

Solicitation of AEs and concomitant medications and symptom-directed physical examination at every visit.

Hematology, serum chemistry, and urinalysis weekly for Cohorts 1 to 3. For **Cohorts 4 to 9** these labs will be collected on dosing days, seven days post dose (starting from Dose 4), at end of study, and ESDD. For **Cohorts 6** CCI these labs will also be collected on Day 2 and two days post dose (starting from Dose 5).

CCI

Urine pregnancy test (for females of childbearing potential) prior to each dose.

Vital signs (blood pressure, pulse, respiration rate and temperature) at all dosing visits.

Subjects will be instructed to contact the site immediately if any flu-like symptoms are noted (eg, fatigue, pyrexia, chills, myalgia, joint pain or headache).

Pharmacokinetics:

Plasma GS-9620 concentrations will be collected at the following time points **for all cohorts**:

- Pre-dose (≤ 5 minutes prior to dosing), 0.5, 1, 2, 4, 6, 8, 10, and 12 hours post dose at Day 1; then one sample 48 hours post dose at Day 3
- **If the SEC approves the dose escalation to 12 mg in Cohort 6, starting from Dose 4 and onwards**, plasma GS-9620 concentrations will also be collected on Day 43 (Dose 4): Pre-dose (≤ 5 minutes prior to dosing), 0.5, 1, 2, 4, 6, 8, 10, and 12 hours post dose; then one sample 48 hours post dose at Day 45

CCI

A single trough ARV PK sample will be collected at Pre-Baseline/Day -13 (**Cohorts 1 to 3**) or at Screening, Day 29, Day 57, Day 85 and Day 99 (**Cohort 5**), or at Screening, Day 57 and Day 99 (**Cohorts 6** CCI CCI

The timing of the ARV trough collection is to be 20-24 hours following the subject's previous QD regimen dose and before next ARV dose (and, for any subject on a regimen containing a BID component, the trough collection must also occur 8-12 hours following the subject's previous dose of that BID component and before next ARV dose). These samples may be analyzed to assess interim ART adherence.

Pharmacodynamics:

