Symptom-directed physical examination, review of AEs and concomitant medications, weight, eGFR, hematology, serum chemistry, urinalysis, urine pregnancy test (for females of childbearing potential, if not performed within the previous 30 days).

Early Study Drug Discontinuation Visit Procedures:

Symptom-directed physical examination, review of AEs and concomitant medications, weight, eGFR, HIV-1 RNA, hematology, serum chemistry, whole blood ISG mRNA panel, serum cytokine/soluble biomarker studies, urinalysis, urine pregnancy test.

Procedure Definitions and Specifications:

HIV-1 RNA will be performed by a licensed assay with a lower limit of quantitation of at least 20 copies/mL.

Hematology panel includes: complete blood count (CBC) with differential and platelets, CD4+ cell count, CD8+ cell count, CD4/CD8 ratio, and CD4%.

Serum chemistry panel includes: alkaline phosphatase, AST, ALT, total and direct bilirubin, total protein, albumin, bicarbonate, BUN, calcium, chloride, creatinine, glucose, phosphate, magnesium, potassium, sodium, CPK, and uric acid.

Urinalysis includes dipstick. **Serum and urine pregnancy tests** are performed only on female subjects of childbearing potential.

Phlebotomy volume limits will be maintained in accordance with American Red Cross blood donation guidelines, which limit blood donation to 473 mL every 56 days. Subjects will undergo periodic phlebotomy over a 149-day period and will provide no more than 473 mL every 56 days. Subjects will be prohibited from blood donation in excess of that required for clinical care within 30 days prior to screening and 30 days after study ends.

Study Treatment:

Investigational Medicinal Products:	GS-9620: 1 mg, 2 mg, 4 mg, 6 mg (administered as three 2 mg tablets), 8 mg (administered as two 4 mg tablets), 10 mg (administered as five 2 mg tablets), 12 mg (administered as six 2 mg tablets, or three 4 mg tablets) dose administered orally once every other week.
Reference Treatment:	Placebo-to-match GS-9620, administered orally once every other week.
Duration of Treatment:	The treatment duration is 71 days (Cohorts 1 to 3), 127 days (Cohorts 4 to 6), CCI [REDACTED]
Other Treatment:	Subjects will continue their existing ARV regimen (as currently prescribed and supplied) for the duration of study participation.

Criteria for Evaluation:

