	Post-Baseline study visits ^c																																
	Day -48	Day -13	Baseline/ Day 1	Day 3	Day 5	Day 8	Day 11	Day 15	Day 17	Day 19	Day 22	Day 25	Day 29	Day 31	Day 33	Day 36	Day 39	Day 43	Day 45	Day 47	Day 50	Day 53	Day 57	Day 59	Day 61	Day 64	Day 67	Day 71	Day 73	Day 75	Day 78	Day 81	Day 101
TLR7 genotyping		X																															
Serum for cytokine/ soluble biomarker studies ¹			X	X		X	X	X		X		X	X		X		X	X		X		X	X		X		X	X		X		X	X
Whole blood ISG mRNA ¹			X	X		X	X	X		X		X	X		X		X	X		X		X	X		X		X	X		X		X	X
Cell associated HIV-1 RNA/DNA with stored PBMCs ¹			X	X													X	X								X	X						X
Plasma HIV-1 RNA Single Copy Assay with stored plasma ¹			X	X													X	X								X	X						X
PBMC – ELISPOT ¹		X																									X						X
Whole blood – immune cell activation ¹			X	X								X	X														X	X					

Study Procedure	Screen ^a	Pre-Baseline	Dose 1 ^b					Dose 2				Dose 3				Dose 4			Dose 5			Dose 6			End of Study	ESDD							
	Post-Baseline study visits ^c																																
	Day -48	Day -13	Baseline/ Day 1	Day 3	Day 5	Day 8	Day 11	Day 15	Day 17	Day 19	Day 22	Day 25	Day 29	Day 31	Day 33	Day 36	Day 39	Day 43	Day 45	Day 47	Day 50	Day 53	Day 57	Day 59	Day 61	Day 64	Day 67	Day 71	Day 73	Day 75	Day 78	Day 81	Day 101
Whole blood - flow FoxP3+ Treg ⁱ			X									X															X						
PBMC ICS for Treg ⁱ			X	X																							X	X					
Review DLTs to confirm dosing can proceed							X					X					X					X					X						
In-Clinic Dosing ^j			X				X					X					X					X					X						

- a Evaluation to be completed within 35 days prior to Pre-Baseline/Day -13
- b Subjects should be administered study drug after Baseline/Day 1 visit assessments (except for post-dose intensive PK)
- c All study visits are to be scheduled relative to the Baseline/Day 1 visit date.
- d Collect ART history for at least 12 months; Pre-ARV viral set point, pre-ARV CD4 nadir and historical genotype will be collected if available
- e Urogenital/anorectal exams may be performed at discretion of the Investigator
- f Symptom-directed physical examination as needed
- g Females of childbearing potential only. Positive urine pregnancy tests will be confirmed with a serum test at any visit. At End of Study visit (Day 101), urine pregnancy test only performed if not done within past 30 days.

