- g Females of childbearing potential only. Positive urine pregnancy tests will be confirmed with a serum test at any visit. At End of Study visit (Day 157), urine pregnancy test only performed if not done within past 30 days.
- h Details of pharmacokinetic blood sampling procedures and sample management for all PK samples in the study will be documented in the Pharmacokinetic Sample Collection, Processing, Storage, and Shipment Manual
- i To be collected pre-dose on dosing days
- j On dosing days, study drug should be taken with approximately 240 mL of water on an empty stomach. Food will not be permitted between at least 2 hours prior to and until 2 hours after dosing. Aside from the 240 mL of water provided at dosing, water/liquids will not be permitted from 1 hour prior to until 2 hours after dosing. If subjects eat prior to the 2 hour fasting period before study drug dosing, no more than a light meal should be eaten (as described in the PK Sample Collection, Processing, Storage, and Shipment Manual).

Study Procedures Table (Cohorts 5 to 9)^a

[figure not shown]
Study Procedure ^a	Screen ^b	Pre-Baseline	Dose ^c	Day 1 Post L	Day 2 Post L	Day 7 Post L	Dose	Day 7 Post L	Dose	Day 2 Post L	Day 7 Post L	Dose	Day 2 Post L	Day 7 Post L	Dose	Day 2 Post L	Day 7 Post L	Dose	Day 2 Post L	Day 7 Post L	Dose	Day 2 Post L	Day 7 Post L	Dose	Day 2 Post L	Day 7 Post L	Dose	Day 2 Post L	Day 7 Post L	End of Stu	ESDI				
	Post-Baseline study visits ^e																																		
	Day 48	Day 13	Baseline Day	Day	Day	Day	Day 1	Day 2	Day 2	Day 3	Day 3	Day 4	Day 4	Day 5	Day 5	Day 5	Day 5	Day 6	Day 7	Day 7	Day 7	Day 8	Day 8	Day 9	Day 9	Day 10	Day 10	Day 11	Day 11	Day 12	Day 12	Day 12	Day 13	Day 15	
Informed Consent	X																																		
Review I/E Criteria		X																																	
Medical History ^f	X	X	X																																
AEs and Con Meds	X	X	X	X	X	X	X	X	X	X	X	X	X	X	X	X	X	X	X	X	X	X	X	X	X	X	X	X	X	X	X	X	X	X	
Complete Physical Exam ^g	X																																		
Symptom Directed Physical Exam ^h		X	X	X	X	X	X	X	X	X	X	X	X	X	X	X	X	X	X	X	X	X	X	X	X	X	X	X	X	X	X	X	X	X	
12-Lead ECG (performed supine)	X																																		
Vital Signs	X		X			X		X			X		X			X		X			X		X		X		X		X						
Weight	X		X																													X	X		
Height	X																																		
Randomization		X																																	
Stool sample for microbiome analysis ⁱ			X																													X	X		

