- h Symptom-directed physical examination as needed
- i [REDACTED]
- j Females of childbearing potential only. Positive urine pregnancy tests will be confirmed with a serum test at any visit. At End of Study visit, urine pregnancy test only performed if not done within past 30 days
- k Details of pharmacokinetic blood sampling procedures and sample management for all PK samples in the study will be documented in the Pharmacokinetic Sample Collection, Processing, Storage, and Shipment Manual.
- l In **Cohorts 5 and 6**, **CCI** [REDACTED], the study drug will be administered following an overnight fast.
CCI [REDACTED]
- m **Cohorts 6** [REDACTED] only
- n **Cohort 6 only**, if dose escalation to 12mg is approved by SEC
- o To be collected pre-dose on dosing days
- p **Cohorts 6** **CCI** only required at Screening, Days 57 and Days 99

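### The urine test taken before the final dose can waive the only scheduled pregnancy test after it, at End of Study

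*Protocol*

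**What the plan says.** The Protocol Synopsis (On-Study Procedures, Safety) requires: "Urine pregnancy test (for females of childbearing potential) prior to each dose". The last of these tests comes before the final dose, on Day 71 (Cohorts 1 to 3) or Day 127 (Cohorts 4 to 9).

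Section 6.5.1 sets the closing visit: "30 days after the last administration of study drug, subjects will return to the study center to complete an end of study visit". The Synopsis gives its window: "The Day 101 and 157 visits have an allowable window of ± 3 days".

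The test at that visit is conditional wherever it is described:

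- Section 6.5.1.4.2: "Urine pregnancy test (females of childbearing potential only, if not done within the previous 30 days".
- Synopsis, Additional End of Study Procedures: "urine pregnancy test (for females of childbearing potential, if not performed within the previous 30 days".
- Appendix 2, Cohorts 1 to 3, footnote g: "At End of Study visit (Day 101), urine pregnancy test only performed if not done within past 30 days".
- Appendix 2, Cohort 4, footnote g: "At End of Study visit (Day 157), urine pregnancy test only performed if not done within past 30 days".
- Appendix 2, Cohorts 5 to 9, footnote j: "At End of Study visit, urine pregnancy test only performed if not done within past 30 days".

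The Early Study Drug Discontinuation visit (Section 6.5.2) also includes a urine pregnancy test, with no such condition, but only for women who stop study drug early.

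**The concern.** The exemption period has the same length as the nominal gap between the last pre-dose test and End of Study, and nothing requires the qualifying test to have been taken after the final dose. A sample that predates the last exposure can therefore cancel the one test that follows it. Whether it does depends on which side of day 30 the visit falls.

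Appendix 5 says that risk in human pregnancy has not been evaluated. Section 7.7.2.1 requires pregnancies found during the follow-up period after study drug to be reported within 24 hours and followed to outcome, and SAP Section 7.6 lists pregnancies during the study. All of this depends on a pregnancy being found. Where the test is waived, the plan relies on the woman recognising or suspecting a pregnancy and saying so. The test guides no further dosing in this study. Its use is to find and follow a pregnancy exposed to the final dose.

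**Working it through.** **Gap between the last pre-dose test and End of Study.** The visit days are from the Synopsis and Appendix 2.

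- Cohorts 1 to 3: 101 − 71 = 30 days.
- Cohorts 4 to 9: 157 − 127 = 30 days.

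Both agree with the 30 days in Section 6.5.1. The ± 3-day window gives gaps of 27 to 33 days, which is 7 permitted days.

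| Days since final dose | Visit day, Cohorts 1–3 | Visit day, Cohorts 4–9 | Waived if 30 counts as *within* | Waived if it does not |
|---|---|---|---|---|
| 27 | 98 | 154 | yes | yes |
| 28 | 99 | 155 | yes | yes |
| 29 | 100 | 156 | yes | yes |
| 30 | 101 | 157 | yes | no |
| 31 | 102 | 158 | no | no |
| 32 | 103 | 159 | no | no |
| 33 | 104 | 160 | no | no |

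The test is waived on 4 of 7 days under the inclusive reading and on 3 of 7 under the strict one. These are counts of calendar days, not probabilities, because the documents do not say how visits will spread over the window.

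**Other tests after the final dose.** In the visible schedules (Protocol Appendix 2; SAP Appendix 2 for Cohorts 5 to 9), no visit between the final dose and End of Study includes a pregnancy test for a woman who completes dosing.

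**Would the End of Study test detect the conceptions that matter?** Protocol Section 1.2.3.1 gives median terminal half-lives of 17.16 to 26.96 h at 1 to 4 mg in healthy subjects. Section 1.4 gives about 8 to 25 h in HBV- or HCV-infected subjects. I assume that higher doses behave similarly. The time for the drug to fall to 1% of its level is half-life × log2(100) / 24, with log2(100) = 6.644:

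- 8 h: 8 × 6.644 / 24 = 2.2 days.
- 17.16 h: 17.16 × 6.644 / 24 = 4.75 days.
- 26.96 h: 26.96 × 6.644 / 24 = 7.46 days.

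A conception as late as that point would have the following age at the earliest permitted visit, day 27:

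- 27 − 7.46 = 19.5 days.
- 27 − 4.75 = 22.2 days.
- 27 − 2.2 = 24.8 days.

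If a urine test turns positive 10 to 14 days after conception (an assumption; the documents give no figure), all of these would be detectable at End of Study. On the same assumption the pre-dose test can miss any conception from 10 to 14 days before the final dose onward.

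**What stays untested even with the change.** Section 4.2, criterion 17, requires contraception for 36 days after the last dose. Between 36 − 33 = 3 and 36 − 27 = 9 of those days fall after End of Study. With the longest half-life, the fraction of drug left at 14 days is 2^(−336/26.96) = 0.018%, so conceptions that late have essentially no exposure.

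**The case against.** Several points can be made for the plan as written.

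- **The wording is consistent, and other safeguards exist.** The condition is the same in all five places, so it reads as a choice and not a slip. Highly effective contraception or abstinence is required, and women must report a suspected as well as a confirmed pregnancy (Section 7.7.2.1; Appendix 5, which words the period after the last dose as 30 days or 4 weeks). End of Study itself includes an adverse event review and a symptom-directed examination. These measures lower the risk, but none of them detects a pregnancy the woman does not suspect. The protocol also tests before every dose despite requiring contraception, so it does not treat contraception as sufficient.
- **The early-discontinuation visit is an imperfect model.** It may fall at any time in the 30 days after the last dose, so a test there can be too early to be informative. That stands. A woman who stops early is scheduled for a test after her last dose, but the timing is not necessarily good. The case for changing End of Study does not depend on the comparison.
- **The yield cannot be quantified.** This also stands. The number of women of childbearing potential is not given, and no endpoint, analysis set or escalation rule depends on the result. It limits the importance of the point, not its correctness.
- **Some text is redacted,** notably for optional Cohorts 7 to 9 and between Sections 6.6 and 6.8. That no other test follows the final dose can be confirmed only on the visible text.

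**Conclusion.** The concern holds. For a woman of childbearing potential who completes dosing, the pre-dose test on Day 71 or Day 127 waives the only visible test after that dose when End of Study falls on days 27 to 29, and on day 30 under the inclusive reading. The day count rests on the schedule alone. The claim that the End of Study test would find the exposed conceptions rests on two assumptions: similar half-lives above 4 mg, and urine positivity 10 to 14 days after conception. The shorter half-life range in Section 1.4 only makes such conceptions older, and so easier to detect, by End of Study. This is a gap in safety follow-up that should be closed. It has no bearing on the efficacy analysis or the sample size.

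**What to change.** Make the End of Study urine pregnancy test unconditional for women of childbearing potential. Delete the 30-day condition in the Synopsis (Additional End of Study Procedures), in Section 6.5.1.4.2, and in the Appendix 2 footnotes: g for Cohorts 1 to 3, g for Cohort 4 and j for Cohorts 5 to 9. The same footnotes are reproduced in SAP Appendix 2 and should be brought into line.

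The cost is a wording change and one urine test per woman at an existing visit where urine is already collected for urinalysis. Every such woman who completes dosing and attends End of Study in its window would then be tested 27 to 33 days after her last dose.

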6.5.1.6.7. Plasma HIV-1 RNA Single Copy Assay with stored plasma

6.5.1.6.8. PBMC for HIV specific T cell response by ELISPOT CCI [REDACTED]

6.5.1.6.9. Serum for cytokine/soluble biomarker studies (Cohorts 1 to 3 only)

6.5.1.6.10. Whole blood ISG mRNA panel (Cohorts 1 to 3 only)

6.5.1.6.11. HIV specific poly-functional T cell ICS (Cohorts 4 to 9). CCI [REDACTED]

6.5.1.6.12. HIV reservoir measurements (Cohorts 4 to 9). CCI [REDACTED]

6.5.1.6.13. CCI [REDACTED]

6.5.2. Early Study Drug Discontinuation Visit (all Cohorts)

Subjects who prematurely discontinue study drug will be required to complete an Early Study Drug Discontinuation Visit (ESDD) within 30 days after their last dose of study treatment.

If a subject discontinues study dosing (for example, as a result of an AE) every attempt should be made to keep the subject in the study and continue to perform the required study-related follow-up and procedures.

At the ESDD Visit, any evaluations showing abnormal results indicating that there is a possible or probable causal relationship with the study drug, should be repeated weekly (or as often as deemed prudent by the Investigator) until the abnormality is resolved, returns to baseline, or is otherwise explained.

The following evaluations are to be completed at the Early Study Drug Discontinuation Visit for all cohorts, unless otherwise specified:

6.5.2.1. Review of AEs and changes in concomitant medication

6.5.2.2. Symptom-directed physical examination as needed

6.5.2.3. Weight

6.5.2.4. Urine collection for the following laboratory procedures:

